Individuals who appear eligible, as determined by the investigative team, will be scheduled to come to the UNC Hospitals for more comprehensive screening. Prior to full screening, individuals will read and sign the informed consent and be given a copy for their records. A breathalyzer test using an Alco-Sensor III breathalyzer machine (Intoximeters, Inc., St. Louis, MO) will be administered (must be 0.00 gms/dl to give informed consent). Height and weight will be measured and BMI calculated. Medical personnel will conduct a medical history and examination including a neurological examination. Over-the-counter and prescription medication use will be recorded. The Fagerstrom Test for Nicotine Dependence (Heatherton et al, 1991) will be administered to smokers. Laboratory evaluations will include complete blood count (CBC) with differential; chemistries including bilirubin, AST, ALT, Alkaline Phosphatase, GGT, sodium, potassium, chloride, blood urea nitrogen, creatinine, and glucose; and urinalysis and urine toxicology. A carbohydrate deficient transferrin (CDT) sample will be drawn. CDT samples will be stored frozen and then shipped in batches of 40 to [name] lab in Charleston, South Carolina for assay. With subjects' permission a sample of blood will also be obtained to archive for possible future genetic analyses. Women will be given a urine pregnancy test (Ub-HCG) at screening and at weeks 4, 8, 12 and 16. Trained interviewers will conduct the psychiatric screening interview using the M.I.N.I. (Sheehan et al., 1999) and the SCID Substance Use Disorders Module to establish DSM-IV criteria for alcohol dependence and to assess for other substance use disorders (First, 2002). The study coordinator will conduct the pretreatment 90-day Timeline Followback interview (TLFB, Sobell et al, 1988) and potential participants will complete the Spielberger State/Trait Anxiety Inventory (SSTAI) (Spielberger et al (1969)), the Drinker's Inventory of Consequences (DrInC, Miller et al, 1995) the FHAM to assess family history of alcohol problems (Rice et al, 1995), the University of Rhode Island Change Assessment Scale (URICA, McConaughy et al, 1989) to assess motivation level, the Penn Alcohol Craving Scale (PACS, Flannery et al 1999) to assess craving, and the Insomnia Severity Index (Bastien et al, 2001) to assess sleep problems. Additionally, potential participants will fill out a short evaluation of their treatment goals. This visit should take about 3 hours.

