### **Initial Treatment Visit**

Individuals meeting all inclusion/exclusion criteria will be informed and scheduled for the initial treatment visit within 10 days. Eligible individuals will not be required to abstain from drinking alcohol prior to randomization though those from Freedom House will be post-detoxification and may be alcohol free. The study coordinator will administer a breathalyzer test (BAC must be  $\leq$ 0.04 gms/d), conduct the TLFB interview, and ask participants to complete the PACS and the SSTAI. The study physician will evaluate withdrawal symptoms using the CIWA-Ar and note the use of medications. A 1-week blister pack of baclofen/placebo with written instructions will be dispensed from the Investigational Drug Services according to the randomization block along with a 1-week back-up blister pack in case of delayed appointments or lost doses. Participants also will be given a calendar style

diary to track pill taking, drinking, and any side effects and a Baclofen Instruction Sheet along with a wallet card detailing potential problems should the individual require emergency medical treatment. Finally, participants will receive Medical Management from a trained clinician. This visit should be completed in about 1.25–1.5 hours.

It is important to uptitrate and downtitrate the dose of baclofen to minimize side-effects. We will parallel the titration schedule used by Franklin et al (2009) in their study of 20 mg of baclofen given four times per day. In the latter study, baclofen was well tolerated without significant differences between baclofen and placebo groups—for the chief side-effect of sedation, the baclofen group had 20 mild, 4 moderate and 0 severe reports of sedation compared to 4 reports of mild sedation and 0 reports of either moderate or severe sedation with placebo (Franklin et al, 2009). Our titration schedule for the 90 mg/d dose is shown in Table 1. The 30 mg/d arm will reach 30 mg/d at day 3 and titrate down starting at day 101.

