## 7 Statistical Plan

### 7.1 Sample Size Determination

Aim 1. Our power calculations are based on the summary scores over the 12 weeks of treatment (%HDD and %ABST). Under our modified design, we must consider our 3 group design. We use Cohen's (1988) effect size definition for standardized difference for our continuous outcomes, coupled with the work of Addolorato et al. (2011) as guidelines for our power estimates and anticipated effect sizes. The Addolorato et al. (2011), similar to our design consists of 2 medication groups and a PBO reference reports contrast of incidence rates between the medication arms and PBO. Thresholds of the size of the contrasts, for comparability to the Cohen guidelines, are as defined by Rosenthal (1996) who parallels Cohen's (1988) terminology of small, medium, and larger effects for qualitative indexes such as Odds ratios and Incidence rates. Addolorato et al. (2011) saw a small to medium effect size for the contrast between PBO and 30mg. Similarly they saw a medium to large effect for the contrast between PBO and 60mg. Replicating a small effect size(Cohen's  $d=0.2$  for our outcomes) for the contrast between PBO and 30mg coupled with a large effect size (Cohen's  $d=0.8$  for our outcomes) for the contrast between PBO and 90mg, provides 82.2% power with 120 participants (40/arm) in testing the overall baclofen effect as well as 84.7% power to contrast 30 mg to 90 mg under the assumed effect sizes. We assume seeing a large effect size for the PBO-90mg is reasonable due to the medium-large effect seen by Addolorato et al. (2011) 60mg-PBO contrast. Interpreting the effect size for our outcomes, the PBO-overall medication contrast corresponds to a difference of 12% in %HD/%ABS rate between PBO and pooled medication sample over the 12 week period under an arc-sine transformation of the observed individual rates. The effect sizes for the contrast between medication arms corresponds to a difference of 19% in %HD/%ABS rates. We experienced 16.2% attrition in Garbutt et al (2010); therefore, a slightly larger effect size would be required to provide sufficient power for the overall BAC effect. Assuming an average effect size of 0.55, corresponds to a difference of 13% in %HDD/%ABS rate between BAC and PBO, we will have power of 82.0% to detect a statistically significant baclofen effect while accounting for attrition and 78.1% power to detect a significant difference between medication levels at the 0.6 effect size accounting for attrition.

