
For Aim 2, our main interest is the moderation effect of pre-treatment drinking rates on the BAC effect during treatment, for which we have some evidence as indicated in our Figure 1. Power calculations of a significant DDD x treatment interaction were implemented through SAS power procedure PROC GLMPOWER. Power derivations depended on an expected effect size, where based on the Addolorato et al. (2002) finding in a sample consisting of more DDD pre-treatment, we expect a large effect for BAC compared to PBO for those(Cohen's  $d > 1$ ), whereas Garbutt et al. (2010) in a sample consisting of lower DDD pre-treatment, found no difference (Cohen's  $d=0$ ). The pattern of this behavior is consistent with Figure 1 where more separation between BAC and PBO is evident in those with higher pre-treatment DDD. To detect this interactive behavior in our proposed design, where we assume an effect size of 1.2 corresponding to a difference of 28% in %HDD/%ABS rates in the Heavy Drinking group, and an effect size of 0 within the non-Heavy drinking group, the study will have 86.7% power to detect a significant interaction between Heavy drinking and BAC assignment. Accounting for 16.2% attrition provides 80.2% power to detect the same effect. Power calculations for the moderation assume 40 per treatment arm, with pre-treatment heavy drinking balanced per arm (20 low and 20 high).

For Aim 3, power is comparable to Aim 1, where we will have 82.2% power to detect a BAC effect for anxiety or an effect size of 0.5 and 82.0% power to detect an effect size of 0.55 while accounting for 16.2% attrition.

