**Primary Efficacy Analysis:** For the Summary measure, we will fit a general linear model on the outcome variable, consisting of main effect for treatment status. Goodness-of-fit, will be analyzed for outliers and influential observations. While these summary measure approaches are simple to implement and commonly used, information concerning the effect of time on the treatment effect is ignored. To understand the impact of time we will also conduct a repeated measures models analysis. From the weekly usage measures we will fit a mixed effects model consisting of main effect for treatment status. This repeated measures approach provides more information about the effect of treatment over time and therefore, more power compared to summary analyses above. We will also include the interaction of time and treatment. The interaction of time and treatment will answer the question as to whether the treatment effect is consistent over the entire treatment period or varies over the weeks. The mixed effects framework offers flexibility for the outcomes, e.g. any usage versus none, or count outcome data, e.g. number of abstinent days (Wolfinger and O'Connell, 1993). Appropriate covariance structure will be determined based on the AIC (Akaike Information Criteria) and BIC (Bayesian Information Criteria). We will evaluate the baclofen effect for changes in CDT using the mixed model approach described above. Within all framework, statistical contrasts will allow us to compare the two levels of BAC to PBO, as well as statistically contrasting the two levels of BAC. The advantage of the statistical contrasts is it allows us to use all available data to estimate the variance (variance-covariance for the repeated measures) of the outcome, while also properly distributing the degrees of freedom for the analytical test to account for the three levels of treatment.

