**Treatment of Missing Data:** With repeated assessments, missing data/attrition is inevitable, but the key thing is that the specified contrasts are not affected due to the presence/absence of data. We will use pattern-mixture models to assess if there is bias due to drop out or missing data (Hedeker and Gibbons, 1997). To address missing data in the survival models, Dupuy and Mesbah(2004) considered jointly modeling time to event data with missing covariate data in order to assess if the missing data is ignorable or non-ignorable. These approaches will be implemented to the fitted cox model. Days in treatment may directly impact the treatment comparison for assessing differences. To control for this potential issue, we will also assess Marginal Structural Cox Regression models (Xiao et al., 2010).

**Adjustment for Covariates:** All modeling approaches allow for the inclusion of covariates. We will include any measures differing at baseline or important potentially confounding measures (i.e. gender, race) in our models to disentangle the intervention effect from these measures

**Specific Aim 2. To test the hypothesis that a history of heavy drinking as assessed by average drinks/drinking day in the 30 days preceding screening predicts baclofen response in alcohol dependence.**

We will include the pre-treatment HDD measure in all models above to examine its predictive merit, as well as its potential moderating impact of the baclofen effect. Moderation effect will be assessed by including the interaction of pre-treatment HDD with the treatment assignment. We will treat pre-

treatment HDD as a continuous measure. We will use mean profile plots based on quartiles of HDD to assess if the continuous measure has a linear, piecewise linear, or curvilinear effect. .

**Specific Aim 3. To test the hypothesis that baclofen, 30 mg/d and 90 mg/d, is superior to placebo in reducing anxiety in alcohol dependence.**

Our analytic procedure is as described in Aim 1 using mixed effects model to account for the repeated measures over time, while contrasting the mean intervention effect as well as assessing the potential moderation effect of pre-treatment HDD.

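### The Aim 3 anxiety model has no pre-specified baseline State anxiety term, although two pre-dose State scores are collected, so power is given up at no saving

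*Combined protocol and SAP*

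**What the plan says.** Section 7.2, Specific Aim 3, carries the Aim 1 method over to anxiety: "Our analytic procedure is as described in Aim 1 using mixed effects model to account for the repeated measures over time". It adds only pre-treatment HDD, a drinking measure, as a possible moderator.

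The Aim 1 model it inherits is described under Primary Efficacy Analysis: "From the weekly usage measures we will fit a mixed effects model consisting of main effect for treatment status". A time-by-treatment interaction follows. No baseline value of the outcome is listed.

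The covariate paragraph of section 7.2 reads "We will include any measures differing at baseline or important potentially confounding measures (i.e. gender, race) in our models". State anxiety is not named there, and no criterion for differing is given.

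Section 6 has participants complete the State/Trait Anxiety Inventory at screening. At the initial treatment visit, where the first blister pack is dispensed, staff "conduct the TLFB interview, and ask participants to complete the PACS and the SSTAI". The Study Schedule of Assessments marks State anxiety at both of these visits and at all ten later ones.

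Section 7.1 sets Aim 3 power equal to that of Aim 1: "we will have 82.2% power to detect a BAC effect for anxiety or an effect size of 0.5", or 82.0% at an effect of 0.55 after 16.2% attrition. It mentions no covariate, significance level or sidedness.

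**The concern.** State anxiety varies from person to person. A pre-dose score explains part of that variation in the on-treatment scores, and without it the variation stays in the error of the treatment contrast. Chance differences in starting anxiety between arms of 40 also move the estimate. Across repeated trials these average to zero, but they widen the interval in each one.

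The covariate rule does not repair this. If the score is added only when "We will include any measures differing at baseline" applies, the model depends on the observed data. Randomization makes such differences rare, so the term would usually be absent. A baseline drinking term is no substitute, because drinking is not the baseline of the anxiety outcome.

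Anxiety is one of two secondary objectives in section 2. The abstract gives it particular prominence among the secondary goals and describes its power as adequate.

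**Working it through.** **Inputs.** Allocation is 40 per arm, so pooled baclofen v placebo is 80 v 40 (section 7.1: "provides 82.2% power with 120 participants (40/arm) in testing the overall baclofen effect"). The standardized effect is 0.5, or 0.55 with 16.2% attrition (section 7.1, Aim 3). The correlation r between the pre-dose State score and the mean on-treatment score is not in the documents; 0.1 to 0.7 is an assumed range.

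**Step 1. Reproduce the printed power, unadjusted.** SE = sqrt(1/40 + 1/80) = 0.1936, and noncentrality = 0.5/0.1936 = 2.582. The noncentral t distribution gives:

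- one-sided 5%: 82.2% (printed 82.2%)
- two-sided 5%: 72.6%

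For attrition, 40 × (1 − 0.162) = 33.5 per arm, taken as 33 v 66. SE = sqrt(1/33 + 1/66) = 0.2132, and noncentrality = 0.55/0.2132 = 2.580. This gives 82.0% one-sided (printed 82.0%) and 72.4% two-sided. The printed figures are therefore unadjusted and correspond to a one-sided 5% test.

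**Step 2. Add the baseline.** Adjustment multiplies the residual variance by (1 − r²), so the effect becomes 0.5/sqrt(1 − r²), at a cost of one degree of freedom. For example, at r = 0.5 it is 0.5/sqrt(0.75) = 0.577, with noncentrality 0.577/0.1936 = 2.98. The equivalent unadjusted sample size is 120/(1 − r²).

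| Assumed r | Two-sided 5% | One-sided 5% | Equivalent unadjusted N |
|---|---|---|---|
| 0 | 72.6% | 82.2% | 120 |
| 0.1 | 73.0% | 82.5% | 121 |
| 0.2 | 74.3% | 83.5% | 125 |
| 0.3 | 76.6% | 85.2% | 132 |
| 0.4 | 79.8% | 87.6% | 143 |
| 0.5 | 84.1% | 90.6% | 160 |
| 0.6 | 89.3% | 94.1% | 188 |
| 0.7 | 94.8% | 97.4% | 235 |

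With attrition (33 v 66, effect 0.55) the two-sided figures are nearly the same: 76.3%, 83.9%, 89.1% and 94.7% at r = 0.3, 0.5, 0.6 and 0.7.

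**Step 3. Test the plan's covariate rule.** The plan gives no threshold, so the simulation assumes the State score is added only if the three arms differ at p < 0.05. In 10,000 simulated trials at two-sided 5%:

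| r | Rule triggered | No term | Rule | Term always in |
|---|---|---|---|---|
| 0.5 | 4.6% | 72.0% | 72.9% | 83.6% |
| 0.7 | 4.9% | 72.2% | 73.7% | 94.4% |

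The rule recovers about 1 to 1.5 points of a possible 12 to 22.

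**Step 4. One baseline score or two.** Assume an equal correlation between any two visits and eight on-treatment scores (weeks 1 to 12). Using the mean of both pre-dose scores instead of one raises r from 0.48 to 0.60 if the between-visit correlation is 0.3, and from 0.67 to 0.77 if it is 0.5.

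**The case against.** The strongest reply is that the plan may already use the pre-dose scores as response time points. No section removes those visits from the anxiety outcome. Section 7.2 also applies the mixed model to changes in CDT, which is drawn only at screening and week 16, so a baseline-as-response layout is plausible there. On that reading the time-by-treatment term would carry a change-from-baseline contrast.

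The plan does not say this for anxiety, and the reading does not do as well. With the Step 4 assumptions, two pre-dose scores and two-sided 5%, the change contrast has 67.4% power against 89.1% for covariate adjustment at a between-visit correlation of 0.3. At 0.5 it is 93.0% against 98.0%, and at 0.6 it is 98.5% against 99.6%. At 0.3 the change contrast is even worse than ignoring baseline (72.6%).

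Several other points stand as limits:

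- The unadjusted contrast is unbiased under randomization, and its standard error already allows for chance imbalance.
- The potential-confounder wording could admit baseline anxiety without an observed difference, but only at someone's discretion.
- The correlation is unknown. Participants from the detoxification centre may have pre-dose scores that reflect recent withdrawal, which could lower it. At r = 0.3 the gain is only 3 points one-sided or 4 two-sided.
- The gap between 72.6% and 82.2% comes from unstated sidedness, not from the missing covariate.
- The calculation compares summary means and does not simulate the full repeated-measures model.

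None of these is a reason to leave the score out: even r = 0.1 repays the degree of freedom.

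**Conclusion.** The point holds. Aim 3 pre-specifies no baseline State anxiety term, and the conditional covariate rule supplies almost none of the missing precision. For the pooled contrast at effect 0.5 with 120 participants, always adjusting adds about 4 points of two-sided power at r = 0.3, 12 at r = 0.5 and 22 at r = 0.7. On the one-sided convention that matches the printed figure, the gains are about 3, 8 and 15 points. If the test is two-sided, adjustment at r of about 0.4 or more is what brings Aim 3 to roughly 80%.

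The sizes rest on the assumed r; the direction does not. The loss is of efficiency, together with a model left open until the data are seen. It is a secondary aim and there is no arithmetic error, so the change is one that should be made and is not critical to the trial.

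**What to change.** In section 7.2, Specific Aim 3, state that every treatment contrast on State anxiety is adjusted for the mean of the screening and initial-visit State scores, whether or not the arms differ at baseline. A constrained baseline model, with equal pre-dose means across arms, is an acceptable alternative. State which scores count as baseline and that pre-dose visits do not contribute to the averaged treatment effect.

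The cost is one or two lines of SAP text and one degree of freedom. It needs no new participants, visits or data.

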## 8 Safety and Adverse Events

### 8.1 Definitions

#### Unanticipated Problems Involving Risk to Subjects or Others

Any incident, experience, or outcome that meets all of the following criteria:

- Unexpected in nature, severity, or frequency (i.e. not described in study-related documents such as the IRB-approved protocol or consent form, the investigators brochure, etc)
- Related or possibly related to participation in the research (i.e. possibly related means there is a reasonable possibility that the incident experience, or outcome may have been caused by the procedures involved in the research,
- Serious (as defined below) “Serious” is different than “severe” as reported in the CTC criteria that applies a grade to the AE.

#### Adverse Event

An **adverse event** (AE) is any symptom, sign, illness or experience that develops or worsens in severity during the course of the study. Intercurrent illnesses or injuries should be regarded as adverse events. Abnormal results of diagnostic procedures are considered to be adverse events if the abnormality:

- results in study withdrawal
- is associated with a serious adverse event
- is associated with clinical signs or symptoms
- leads to additional treatment or to further diagnostic tests
- is considered by the investigator to be of clinical significance

#### Serious Adverse Event

Adverse events are classified as serious or non-serious. A **serious adverse event** is any AE that is:

- fatal
- life-threatening
- requires or prolongs hospital stay
- results in persistent or significant disability or incapacity
- a congenital anomaly or birth defect
- an important medical event

Important medical events are those that may not be immediately life threatening, but are clearly of major clinical significance. They may jeopardize the subject, and may require intervention to prevent one of the other serious outcomes noted above. For example, drug overdose or abuse, a seizure that did not result in in-patient hospitalization, or intensive treatment of bronchospasm in an emergency department would typically be considered serious.

All adverse events that do not meet any of the criteria for serious should be regarded as ***non-serious adverse events***.

For the purpose of this trial the following events are expected side effects of the drug:

- Drowsiness
- Weakness
- Dizziness/lightheadedness
- Nausea/vomiting
- Headache
- Insomnia
- Lethargy/fatigue
- Frequent urination
- Constipation
- Confusion
- Hypotension
- Blurred vision
- Seizures (rare)

#### **Adverse Event Reporting Period**

The study period during which adverse events must be reported is normally defined as the period from the initiation of any study procedures to the end of the study treatment follow-up. For this study, the study treatment follow-up is defined as 30 days following the last administration of study treatment.

#### **Preexisting Condition**

A preexisting condition is one that is present at the start of the study. A preexisting condition should be recorded as an adverse event if the frequency, intensity, or the character of the condition worsens during the study period.

